12.6.1 Consent Process for Adults Who Lack Capacity to Consent to Research Participation

For participants addressed in section [12.3](#), an LAR will be identified consistent with Policy 403 and informed consent obtained from the LAR, as described in Section [12.6](#).

13 REGULATORY AND OPERATIONAL CONSIDERATIONS

13.1 STUDY DISCONTINUATION AND CLOSURE

This study may be temporarily suspended or prematurely terminated if there is sufficient reasonable cause. Written notification, documenting the reason for study suspension or termination, will be provided by the suspending or terminating party to study participants, investigator, funding agency, the Investigational New Drug (IND) sponsor, and regulatory authorities. If the study is prematurely terminated or suspended, the Principal Investigator (PI) will promptly inform study participants, the Institutional Review Board (IRB), and the sponsor, and will provide the reason(s) for the termination or suspension. Study participants will be contacted, as applicable, and be informed of changes to the study visit schedule.

Circumstances that may warrant termination or suspension include, but are not limited to:

- Determination of unexpected, significant, or unacceptable risk to participants
- Demonstration of efficacy that would warrant stopping
- Insufficient compliance to protocol requirements
- Data that are not sufficiently complete and/or evaluable
- Determination that the primary endpoint has been met

*CC Protocol #: 14-C-0156
Abbreviated Title: LY Chk1/2 Inhibitor
Amendment Version Date: 12/02/2020*

- Determination of futility

Study may resume once concerns about safety, protocol compliance, and data quality are addressed, and satisfy the sponsor, IRB and as applicable, Food and Drug Administration (FDA).

13.2 QUALITY ASSURANCE AND QUALITY CONTROL

Each clinical site will perform internal quality management of study conduct, data and biological specimen collection, documentation and completion. An individualized quality management plan will be developed to describe a site's quality management.

Quality control (QC) procedures will be implemented beginning with the data entry system and data QC checks that will be run on the database will be generated. Any missing data or data anomalies will be communicated to the site(s) for clarification/resolution.

Following written Standard Operating Procedures (SOPs), the monitors will verify that the clinical trial is conducted and data are generated and biological specimens are collected, documented (recorded), and reported in compliance with the protocol, International Conference on Harmonisation Good Clinical Practice (ICH GCP), and applicable regulatory requirements (e.g., Good Laboratory Practices (GLP), Good Manufacturing Practices (GMP)).

The investigational site will provide direct access to all trial related sites, source data/documents, and reports for the purpose of monitoring and auditing by the sponsor, and inspection by local and regulatory authorities.

13.3 CONFLICT OF INTEREST POLICY

The independence of this study from any actual or perceived influence, such as by the pharmaceutical industry, is critical. Therefore, any actual conflict of interest of persons who have a role in the design, conduct, analysis, publication, or any aspect of this trial will be disclosed and managed. Furthermore, persons who have a perceived conflict of interest will be required to have such conflicts managed in a way that is appropriate to their participation in the design and conduct of this trial. The study leadership in conjunction with the National Cancer Institute has established policies and procedures for all study group members to disclose all conflicts of interest and will establish a mechanism for the management of all reported dualities of interest.

CC Protocol #: 14-C-0156

Abbreviated Title: LY Chk1/2 Inhibitor

Amendment Version Date: 12/02/2020

13.4 CONFIDENTIALITY AND PRIVACY

Participant confidentiality and privacy is strictly held in trust by the participating investigators, their staff, and the sponsor(s). This confidentiality is extended to cover testing of biological samples and genetic tests in addition to the clinical information relating to participants. Therefore, the study protocol, documentation, data, and all other information generated will be held in strict confidence. No information concerning the study or the data will be released to any unauthorized third party without prior written approval of the sponsor.

All research activities will be conducted in as private a setting as possible.

The study monitor, other authorized representatives of the sponsor, representatives of the Institutional Review Board (IRB), and/or regulatory agencies may inspect all documents and records required to be maintained by the investigator, including but not limited to, medical records (office, clinic, or hospital) and pharmacy records for the participants in this study. The clinical study site will permit access to such records.

The study participant's contact information will be securely stored at the/each clinical site for internal use during the study. At the end of the study, all records will continue to be kept in a secure location for as long a period as dictated by the reviewing IRB, Institutional policies, or sponsor requirements.

Study participant research data, which is for purposes of statistical analysis and scientific reporting, will be stored at the NCI CCR. This will not include the participant's contact or identifying information. Rather, individual participants and their research data will be identified by a unique study identification number. The study data entry and study management systems used by the clinical site and by NCI CCR research staff will be secured and password protected. At the end of the study, all study databases will be archived at the NIH.

To further protect the privacy of study participants, a Certificate of Confidentiality has been issued by the National Institutes of Health (NIH). This certificate protects identifiable research information from forced disclosure. It allows the investigator and others who have access to research records to refuse to disclose identifying information on research participation in any civil, criminal, administrative, legislative, or other proceeding, whether at the federal, state, or local level. By protecting researchers and institutions from being compelled to disclose information that would identify research participants, Certificates of Confidentiality help achieve the research objectives and promote participation in studies by helping assure confidentiality and privacy to participants.

CC Protocol #: 14-C-0156
Abbreviated Title: LY Chk1/2 Inhibitor
Amendment Version Date: 12/02/2020

14 PHARMACEUTICAL INFORMATION

14.1 LY2606368

14.1.1 Source

LY2606368 is an investigational agent (IND #123172) and will be supplied to the NIH Clinical Center by Eli Lilly and Company (Indianapolis, IN).

14.1.2 Toxicity

As of 04 April 2016, data were available from 210 patients who were treated with LY2606368 on Schedule 1 or 2. PK data are available from 194 patients from 3 ongoing clinical trials (studies JTJA, JTJF, and JTJK). Study JTJA is the first-in-human phase 1 study of LY2606368.

Hematologic Toxicity

Neutropenia is the most frequent toxicity in study JTJA and has been observed at all doses and schedules of LY2606368.

Prophylactic granulocyte colony stimulating factor (G-CSF) use is permitted as indicated in [**3.3.1.1**](#).

Non-Hematologic Toxicity

The only non-hematologic treatment-emergent AEs (TEAEs) occurring in greater than 10% of patients and deemed by the investigators to be related to LY2606368 treatment (combined Schedule 1 and Schedule 2) were nausea (15%, grade 1: 14%, grade 2: 1%) and fatigue (29%, grade 1/2: 27%, grade 3: 2%). Related non-hematologic TEAEs occurring in 5% to 10% of patients included: anorexia (8%), headache (7%), oral mucositis (7%), diarrhea (5%), and vomiting (5%). All of these were grade 1 or 2.

Cardiovascular Effects

Please see [**3.3.2**](#) QTc Prolongation.

No corrected QT interval (QTc) prolongation was observed in dogs at doses up to 10 mg/kg (200 mg/m²). The mean maximum plasma concentration (C_{max}) levels at the dose at which QTc prolongation was seen in dogs (6950 and 5862 ng/mL at 40 mg/kg, or 800

CC Protocol #: 14-C-0156

Abbreviated Title: LY Chk1/2 Inhibitor

Amendment Version Date: 12/02/2020

mg/m², given as a 1- or 2-hour infusion, respectively) are significantly greater than the largest mean LY2606368 C_{max} in humans at the MTD of 40 mg/m² administered on days 1 to 3 every 14 days (Schedule 1) (cohort mean = 347 ng/mL on day 3 of cycle 1 from Part A in the current phase I study [dose escalation]), and the largest mean LY2606368 C_{max} in humans at the MTD of 105 mg/m² administered on day 1 every 14 days (cohort mean = 867 ng/mL on day 1 of cycle 2 from Part A in the current phase I study).

Abbreviated Title: LY Chk1/2 Inhibitor

Amendment Version Date: 12/02/2020

below). The toxicities have been consistent with either radiation, LY2606368, or cetuximab/cisplatin. During palliative radiation, a break in LY2606368 therapy is allowed not to overlap the therapies. Currently, the estimated median terminal half-life of LY2606368 is 27 hours.

CC Protocol #: 14-C-0156

Abbreviated Title: LY Chk1/2 Inhibitor

Amendment Version Date: 12/02/2020

Table 7 Treatment-Emergent Adverse Events Related to Study Treatment Occurring in ≥ 2 Patients in Each Treatment Group in Study**I4D-MC-JTJI**

Preferred Term	Prexasertib with Cisplatin and Radiation (N=7) n (%)		Prexasertib with Cetuximab and Radiation (N=7) n (%)		Total (N=14) n (%)	
	All Grades	Grade 3/4/5	All Grades	Grade 3/4/5	All Grades	Grade 3/4/5
Radiation skin injury	5 (71.4)	0	6 (85.7)	2 (28.6)	11 (78.6)	2 (14.3)
Anaemia	5 (71.4)	1 (14.3)	4 (57.1)	0	9 (64.3)	1 (7.1)
Dry mouth	4 (57.1)	0	5 (71.4)	0	9 (64.3)	0
Stomatitis	3 (42.9)	2 (28.6)	6 (85.7)	4 (57.1)	9 (64.3)	6 (42.9)
Platelet count decreased	6 (85.7)	0	3 (42.9)	0	9 (64.3)	0
Neutrophil count decreased	6 (85.7)	5 (71.4)	2 (28.6)	2 (28.6)	8 (57.1)	7 (50.0)
Dysphagia	3 (42.9)	1 (14.3)	4 (57.1)	2 (28.6)	7 (50.0)	3 (21.4)
Weight decreased	2 (28.6)	0	5 (71.4)	0	7 (50.0)	0
Nausea	4 (57.1)	0	2 (28.6)	0	6 (42.9)	0
Dermatitis acneiform	0	0	5 (71.4)	4 (57.1)	5 (35.7)	4 (28.6)
Febrile neutropenia	3 (42.9)	1 (14.3)	1 (14.3)	1 (14.3)	4 (28.6)	2 (14.3)
Sinus tachycardia	2 (28.6)	0	2 (28.6)	0	4 (28.6)	0
Hyponatraemia	3 (42.9)	1 (14.3)	1 (14.3)	0	4 (28.6)	1 (7.1)
Aphasia	2 (28.6)	2 (28.6)	2 (28.6)	1 (14.3)	4 (28.6)	3 (21.4)
Vomiting	3 (42.9)	0	1 (14.3)	0	4 (28.6)	0
Fatigue	2 (28.6)	0	2 (28.6)	0	4 (28.6)	0
Mucosal infection	2 (28.6)	0	2 (28.6)	0	4 (28.6)	0
Alanine aminotransferase increased	2 (28.6)	0	2 (28.6)	0	4 (28.6)	0
Aspartate aminotransferase increased	2 (28.6)	0	2 (28.6)	0	4 (28.6)	0
Blood creatinine increased	2 (28.6)	0	1 (14.3)	0	3 (21.4)	0

CC Protocol #: 14-C-0156

Abbreviated Title: LY Chk1/2 Inhibitor

Amendment Version Date: 12/02/2020

Preferred Term	Prexasertib with Cisplatin and Radiation (N=7) n (%)		Prexasertib with Cetuximab and Radiation (N=7) n (%)		Total (N=14) n (%)	
	All Grades	Grade 3/4/5	All Grades	Grade 3/4/5	All Grades	Grade 3/4/5
White blood cell count decreased	2 (28.6)	0	1 (14.3)	0	3 (21.4)	0
Tinnitus	2 (28.6)	0	0	0	2 (14.3)	0
Lymphocyte count decreased	2 (28.6)	0	0	0	2 (14.3)	0
Dyspepsia	0	0	2 (28.6)	0	2 (14.3)	0
Infusion related reaction	0	0	2 (28.6)	0	2 (14.3)	0
Headache	0	0	2 (28.6)	0	2 (14.3)	0

Source: /lillyce/prd/ly2606368/cibjan2017/output/i4d_mc_jtji/smteaepstsoc and smteaepstsocmax.

14.1.3 Formulation and preparation

The drug product, LY2606368 for injection, is supplied for clinical trial use as a lyophilized, yellow to white solid, in glass vials and is composed of LY2606368 mesylate monohydrate and the inactive ingredient Captisol®. Each vial contains 20 mg or 40 mg of the base compound LY2606368. The vial contains a 5% excess to facilitate the withdrawal of the label amount, 20 mg/vial or 40 mg/vial for application with an appropriate device, such as an infusion set.

LY2606368 will be infused through a low-sorbing, polyolefin-lined administration set with in-line 0.2-micrometer polyethersulfone filter. All components must be DEHP-free.

Patients will receive LY2606368 at the RP2D of 105 mg/m² IV once every 14 days of a 28-day cycle.

Reconstituting the vial contents with 10 mL of water gives a clear yellow solution with a concentration of 2 mg/mL of LY2606368, pH 4 to 7, and an osmotic pressure ratio of 344 mOsm.

CC Protocol #: 14-C-0156

Abbreviated Title: LY Chk1/2 Inhibitor

Amendment Version Date: 12/02/2020

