14.1.5 Administration procedures

LY2606368 dose MAY be recalculated during repeated treatment cycles as a function of minor changes in body weight measurements through time. Dose recalculation during repeated treatment cycles is REQUIRED only when a patient's weight changes +/- 10% or more from their body weight measured just before starting study treatment (baseline weight).

LY2606368 is administered as an IV infusion over 1hour (+/-10min) using a central or free flowing peripheral IV line with an appropriate filter. Subsequent infusion may be extended if infusion over 1hr was not well tolerated, including but not limited to grade 1 facial flushing. LY2606368 should not come in contact with normal saline. The patient's vascular access device should be flushed with dextrose 5% injection (D5W) before and after LY2606368 administration.

The reconstituted drug product from the vials should be diluted with Dextrose 5% Injection (D5W) to a final volume of no more than 250 ml. If less than 250 ml is used, the concentration of LY2606368 must be maintained within a range of 0.08 mg/mL to 1.60 mg/mL of LY2606368.

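### Section 14.1.3 gives one reconstitution volume and one concentration for two vial strengths; the figures cannot hold for the 40 mg vial, and relying on them could double the dose drawn

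*Combined protocol and SAP*

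**What the plan says.** Section 14.1.3 (Formulation and preparation) names two presentations: "Each vial contains 20 mg or 40 mg of the base compound LY2606368". It repeats both when describing the overfill: "The vial contains a 5% excess to facilitate the withdrawal of the label amount, 20 mg/vial or 40 mg/vial". It gives the dose as 105 mg/m² every 14 days, and then makes a single reconstitution statement: "Reconstituting the vial contents with 10 mL of water gives a clear yellow solution with a concentration of 2 mg/mL of LY2606368". That statement is not tied to either strength.

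Section 14.1.5 (Administration procedures) covers only the later dilution: "The reconstituted drug product from the vials should be diluted with Dextrose 5% Injection (D5W) to a final volume of no more than 250 ml". For volumes below 250 mL it adds that "the concentration of LY2606368 must be maintained within a range of 0.08 mg/mL to 1.60 mg/mL of LY2606368". Neither section gives a separate reconstitution volume or concentration for the 40 mg vial, or refers to a pharmacy manual that would override the text.

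**The concern.** Content, volume and concentration are linked by one division, so a single volume and a single concentration cannot both be true of two vials whose contents differ by a factor of two. The protocol contains no other conversion from milligrams to millilitres of reconstituted drug.

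A preparer who follows the text with 40 mg vials, and converts the dose to a volume at the stated concentration, would draw twice the intended amount. Section 1.2 gives 105 mg/m² as the maximum tolerated dose on this schedule. Table 1 shows 130 mg/m² as the highest dose tested on it, and Table 2 lists dose-limiting toxicities at 120 and 130 mg/m². A twofold error therefore matters at the starting dose, and it could also undo the protocol's dose reductions.

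**Working it through.** **Inputs**

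- Vial content on the label: 20 mg or 40 mg (Section 14.1.3)
- Overfill: 5%, so 21 mg or 42 mg (Section 14.1.3)
- Reconstitution volume 10 mL; stated concentration 2 mg/mL (Section 14.1.3)
- Dose levels: 105, 80 and 60 mg/m² (Section 3.1, Table 4)
- Largest infusion volume 250 mL; permitted range 0.08 to 1.60 mg/mL when less than 250 mL is used (Section 14.1.5)
- BSA: not given for this trial's participants. I assume 1.7 m² for illustration and checked 1.5 to 2.0 m².

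**Step 1. Reproduce the stated concentration** (content / volume)

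| Vial | Label content | With 5% excess | Stated |
|---|---|---|---|
| 20 mg | 20/10 = 2.0 mg/mL | 21/10 = 2.1 mg/mL | 2 mg/mL |
| 40 mg | 40/10 = 4.0 mg/mL | 42/10 = 4.2 mg/mL | 2 mg/mL |

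The stated figure reproduces for the 20 mg vial. For the 40 mg vial it is off by exactly a factor of two on label content, so neither rounding nor overfill explains it.

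**Step 2. Effect on the amount drawn**

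If the volume is calculated as dose / 2 mg/mL and the solution is actually 4 mg/mL, then

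amount drawn / dose = (dose / 2) × 4 / dose = 2.

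BSA and dose level cancel. At 105 mg/m² and 1.7 m²:

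- intended dose: 105 × 1.7 = 178.5 mg
- volume drawn: 178.5 / 2 = 89.25 mL
- content at 4 mg/mL: 89.25 × 4 = 357 mg
- equivalent dose: 357 / 1.7 = 210 mg/m²

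At the lowest level, 60 mg/m², the doubled dose is 2 × 60 = 120 mg/m².

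If a share *f* of the volume comes from 40 mg vials, the factor is (4*f* + 2(1 − *f*)) / 2 = 1 + *f*: 1.0 at *f* = 0, 1.5 at *f* = 0.5 and 2.0 at *f* = 1. Counting the overfill, the upper end is 4.2 / 2 = 2.1.

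**Step 3. Would the concentration limits reveal it?**

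A preparer who believes the solution is 2 mg/mL checks the nominal value: 178.5 / 250 = 0.71 mg/mL, well inside the range. The true value is 357 / 250 = 1.43 mg/mL, also inside it. In 250 mL, the true concentration of a doubled 105 mg/m² dose passes 1.60 mg/mL only above a BSA of 1.60 × 250 / (2 × 105) = 1.90 m². At 1.7 m² it passes 1.60 mg/mL once the final volume falls below 357 / 1.60 = 223 mL. In either case the excess is visible only to someone who already knows the true content.

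**The case against.** The arithmetic is not in dispute; the argument on the other side is about consequence.

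- **The sentence describes the solution rather than telling staff how to draw a dose.** It sits alongside colour, pH and osmotic figures, and the same section speaks of withdrawing the label amount. Counting label milligrams per vial would avoid the error. This stands, and it is why the dose effect is conditional. It does not make the sentence true, and nothing else in the protocol supplies the conversion.
- **The error needs several things at once, and there is a visible check.** It requires 40 mg vials, 10 mL in each, and a volume calculated at 2 mg/mL. Drawing 89.25 mL would mean opening 9 vials labelled 40 mg (360 mg in all) for a 178.5 mg dose, when 5 vials (200 mg) would cover it. An attentive pharmacist could notice. This also stands, but it depends on staff not relying on the text.
- **Twofold is the worst case.** Correct: mixed strengths give a factor between 1 and 2.
- **The limits in Section 14.1.5 apply only below 250 mL, and could be exceeded in some cases.** Correct, so the claim is that they would not reliably expose the error, not that they never could.
- **Pharmacy materials outside the documents may already separate the strengths.** Possible, and it cannot be checked here. The likelihood of an actual error is therefore unknown.

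**Conclusion.** The point holds. As written, the reconstitution statement is false for one of the two vial strengths that the same section names, by a factor of two on label content. That finding needs no assumption.

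The dose consequence is conditional. It reaches a factor of 2 on label content (2.1 with the overfill) if the whole dose comes from 40 mg vials reconstituted in 10 mL and the volume is calculated at 2 mg/mL. The factor does not depend on BSA; only the illustrative milligram amounts and the 0.71 and 1.43 mg/mL figures rest on the assumed 1.7 m². The documents do not show that an error was made, which strength was dispensed, or which of the stated figures is the wrong one.

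The point does not touch the endpoint, sample size or decision rules. I still class it as a must-fix because it concerns the preparation of an intravenous drug started at its maximum tolerated dose, and because the correction is small.

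**What to change.** Reconcile Section 14.1.3 with the drug supplier's preparation instructions. For each vial strength, state the diluent volume and the resulting concentration, and say whether the 5% excess is counted, so that mg, mL and mg/mL agree. If only one strength is used in this trial, say so and limit the statement to it. Any pharmacy preparation worksheet should be checked against the corrected text. This review does not propose which volume or concentration applies.

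The cost is one or two sentences in Section 14.1.3 and the worksheet check. The analysis is unaffected.

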14.1.4 Stability and Storage

The drug product is stable when stored at room temperature.

The reconstituted formulation is stable for at least 24 hours at room temperature; however, since the reconstituted drug product does not contain a preservative, the unused solution must be discarded after 12 hours.

14.1.5 Administration procedures

LY2606368 dose MAY be recalculated during repeated treatment cycles as a function of minor changes in body weight measurements through time. Dose recalculation during repeated treatment cycles is REQUIRED only when a patient's weight changes +/- 10% or more from their body weight measured just before starting study treatment (baseline weight).

LY2606368 is administered as an IV infusion over 1hour (+/-10min) using a central or free flowing peripheral IV line with an appropriate filter. Subsequent infusion may be extended if infusion over 1hr was not well tolerated, including but not limited to grade 1 facial flushing. LY2606368 should not come in contact with normal saline. The patient's vascular access device should be flushed with dextrose 5% injection (D5W) before and after LY2606368 administration.

The reconstituted drug product from the vials should be diluted with Dextrose 5% Injection (D5W) to a final volume of no more than 250 ml. If less than 250 ml is used, the concentration of LY2606368 must be maintained within a range of 0.08 mg/mL to 1.60 mg/mL of LY2606368.

14.1.6 Incompatibilities

LY2606368 is incompatible with solutions containing saline or lactated Ringer and must not be mixed or administered simultaneously with other drugs through the same infusion line.

16 APPENDICES

16.1 APPENDIX A – PERFORMANCE STATUS CRITERIA

ECOG Performance Status Scale		Karnofsky Performance Scale	
Grade	Descriptions	Percent	Description
0	Normal activity. Fully active, able to carry on all pre-disease performance without restriction.	100	Normal, no complaints, no evidence of disease.
		90	Able to carry on normal activity; minor signs or symptoms of disease.
1	Symptoms, but ambulatory. Restricted in physically strenuous activity, but ambulatory and able to carry out work of a light or sedentary nature (e.g., light housework, office work).	80	Normal activity with effort; some signs or symptoms of disease.
		70	Cares for self, unable to carry on normal activity or to do active work.
2	In bed <50% of the time. Ambulatory and capable of all self-care, but unable to carry out any work activities. Up and about more than 50% of waking hours.	60	Requires occasional assistance, but is able to care for most of his/her needs.
		50	Requires considerable assistance and frequent medical care.
3	In bed >50% of the time. Capable of only limited self-care, confined to bed or chair more than 50% of waking hours.	40	Disabled, requires special care and assistance.
		30	Severely disabled, hospitalization indicated. Death not imminent.

CC Protocol #: 14-C-0156

Abbreviated Title: LY Chk1/2 Inhibitor

Amendment Version Date: 12/02/2020

4	100% bedridden. Completely disabled. Cannot carry on any self-care. Totally confined to bed or chair.	20	Very sick, hospitalization indicated. Death not imminent.
		10	Moribund, fatal processes progressing rapidly.
5	Dead.	0	Dead.

CC Protocol #: 14-C-0156

Abbreviated Title: LY Chk1/2 Inhibitor

Amendment Version Date: 12/02/2020

16.2 APPENDIX B - DRUGS KNOWN TO CAUSE QT PROLONGATION AND/OR INDUCE TORSADES DE POINTES

Generic Name	Brand Names	Drug Class	Therapeutic Use
Amiodarone	Cordarone®, Pacerone®, Nexterone®	Anti-arrhythmic	Abnormal heart rhythm
Anagrelide	Agrylin®, Xagrid®	Phosphodiesterase 3 inhibitor	Thrombocythemia
Arsenic trioxide	Trisenox®	Anti-cancer	Leukemia
Azithromycin	Zithromax®, Zmax®	Antibiotic	Bacterial infection
Chloroquine	Aralen®	Anti-malarial	Malaria infection
Chlorpromazine	Thorazine®, Largactil®, Megaphen®	Anti-psychotic / Anti-emetic	Schizophrenia/ nausea
Citalopram	Celexa®, Cipramil®	Anti-depressant, SSRI	Depression
Clarithromycin	Biaxin®, Prevpac®	Antibiotic	Bacterial infection
Cocaine	Cocaine	Local anesthetic	Topical anesthetic
Disopyramide	Norpace®	Anti-arrhythmic	Abnormal heart rhythm
Dofetilide	Tikosyn®	Anti-arrhythmic	Abnormal heart rhythm
Dronedarone	Multaq®	Anti-arrhythmic	Atrial Fibrillation
Droperidol	Inapsine®, Droleptan®, Dridol®, Xomolix®	Anti-psychotic / Anti-emetic	Anesthesia adjunct, nausea
Erythromycin	EES®, MY-E®, Robimycin®, EMycin®, Erymax®, Ery-Tab®, Eryc Ranbaxy®, Erypar®, Eryped®, Erythrocin Stearate Filmtab®, Erythrocot®, E-Base®, Erythroped®, Illosone®, Pediamycin®, Zinergy®, Abbotycin®,	Antibiotic	Bacterial infection; increase GI motility

CC Protocol #: 14-C-0156

Abbreviated Title: LY Chk1/2 Inhibitor

Amendment Version Date: 12/02/2020

	Abbotycin-ES®, Erycin®, PCE Dispertab®, Stiemycine®, Acnasol®, Tiloryth®		
Escitalopram	Cipralex®, Lexapro®, Nexito®, Seroplex®, Elicea®, Lexamil®, Lexam®, [Anxiset-E®, Exodus®, Esto®, Entact®, Losita®, Reposil®, Animaxen®, Esitalo®, Lexamil® (Not available in the US)]	Anti-depressant, SSRI	Major depression/ Anxiety disorders
Generic Name	Brand Names	Drug Class	Therapeutic Use
Flecainide	Tambocor®, Almarytm®, Apocard®, Ecrinal®, Flécaïne®	Anti-arrhythmic	Abnormal heart rhythm
Halofantrine	Halfan®	Anti-malarial	Malaria infection
Haloperidol	Aloperidin®, Bioperidolo®, Brotopon®, Dozic®, Einalon S®, Eukystol®, Halosten®, Keselan®, Linton®, Peluces®, Serenace®, Serenase®, Sigaperidol®, Haldol® (US & UK), Duraperidol® (Germany),	Anti-psychotic	Schizophrenia, agitation
Ibutilide	Corvert®	Anti-arrhythmic	Abnormal heart rhythm
Methadone	Dolophine®, Symoron®, Amidone®, Methadose®, Physeptone®, Heptadon®	Opiate	Pain control, narcotic dependence
Moxifloxacin	Avelox®, Avalox®, Avelon®	Antibiotic	Bacterial infection
Ondansetron	Zofran®, Anset®, Ondemet®, Zuplenz®, Emetron®, Ondavell®, Emeset®, Ondisolv®, Setronax®	Anti-emetic	Nausea, vomiting
Pentamidine	NebuPent®, Pentam®	Antibiotic	Pneumocystis pneumonia
Pimozide	Orap®	Anti-psychotic	Tourette's tics
Procainamide (Oral off US mkt)	Pronestyl®, Procan®	Anti-arrhythmic	Abnormal heart rhythm
Quinidine	Quinaglute®, Duraquin®, Quinact®, Quinidex®, Cin-Quin®, Quinora®	Anti-arrhythmic	Abnormal heart rhythm

CC Protocol #: 14-C-0156

Abbreviated Title: LY Chk1/2 Inhibitor

Amendment Version Date: 12/02/2020

Sevoflurane	Ulane®, Sojourn®	Anesthetic, general	Anesthesia
Sotalol	Betapace®, Sotalex®, Sotacor®	Anti-arrhythmic	Abnormal heart rhythm
Thioridazine	Mellaril®, Novoridazine®, Thioril®	Anti-psychotic	Schizophrenia
Vandetanib	Caprelsa®	Anti-cancer	Thyroid cancer

Source: www.QTdrugs.org Updated September 2013.

CC Protocol #: 14-C-0156

Abbreviated Title: LY Chk1/2 Inhibitor

Amendment Version Date: 12/02/2020

